Surgical Site Occurrences (SSO) has been defined in this study as the following AEs: Seroma, Hematoma, Surgical Site Infection, and bleeding at tack implantation site. These events were chosen based on previous clinical studies and tailored to the type of events that could occur due to fixation, including tacks ⁽²⁵⁾. Though other events may occur in a subject, these SSOs (beyond hernia recurrence) are the events of interest for this study.

The visit windows for the Month 1, 3, and 12 visits all open on the target date (e.g., Month 1 window begins at 30 days) rather than the allowance for windows to open early. The visit windows are designed to ensure accurate capture of what occurred within that timeframe rather than evaluating the endpoints too early (e.g., within 3 months).

Claims to be verified:

The AFFIX study will verify the following relevant claims related to MaxTack[™]:

- Positive clinical outcomes for fixation of prosthetic material to soft tissue in minimally invasive ventral hernia repair procedures compared to State Of The Art expressed by:
 - the hernia recurrence rate
 - the change in subject Quality of Life (QoL), as measured through the administration o the Hernia Quality of Life Survey (HerQLes) questionnaire (Section 18.4 Appendix D – HerQLes Quality of Life Questionnaire), evaluated at screening and compared to other timepoints
 - the change in subject-reported pain score at the hernia site evaluated with the Numeric Rating Scale (NRS) (Section 18.3 Appendix C – Pain Numerical Rating Scale) at screening compared to other timepoints
- Ability to accommodate physicians in their surgical techniques and clinical cases by enabling prosthetic material fixation to soft tissue: ease of use, compatibility with minimally invasive surgical approach(es) assessed using the Surgeon Satisfaction Questionnaire (Section 18.8 Appendix H – Surgeon Satisfaction Questionnaire).

7. Product Description

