9.3 Exclusion Criteria

Subjects will be excluded from the study if they meet any of the following criteria:

Preoperative Exclusion Criteria:

- 1. Subject is undergoing an emergency surgery (e.g., lifesaving procedures performed where subject is in imminent danger of death, strangulated hernia, etc.)
- 2. Subject has history of 3 or more hernia repair procedures
- 3. Subject has existing mesh in the space where the physician needs to apply the new mesh to be fixated with the MaxTack[™] Motorized Fixation Device
- 4. Subject is scheduled (or anticipated to be scheduled) for additional surgery, and subsequent surgery would jeopardize previous application of study treatment
- 5. Subject has history of allergic reactions to Poly (Glycolide-co-L-IActide) (PGLA)
- 6. Subject has history of allergic reactions to the components of the intended mesh
- 7. Subject has any systemic or local ongoing infection at the time of the surgery
- 8. Subject has a Body Mass Index (BMI) greater than 45 kg/m²
- 9. Subject has life expectancy in the opinion of the investigator, of less than 3 years at the time of enrollment
- 10. Subject is pregnant (as determined by standard site practices) or is planning to become pregnant during study duration period.
- 11. Subject has participated or will participate in an investigational drug or device research study that would interfere with the results of this study
- 12. Subject's participation in the study may jeopardize the safety or welfare of the subject, as determined by the investigator
- 13. Subject is already enrolled or was previously enrolled in this study

Intraoperative Exclusion Criteria:

1. Subject did not receive the MaxTack[™] Motorized Fixation Device tacks to fixate the mesh

AFFIX (MaxTac Clinical Investi				
MDT23014	Revision	3.0	Page 35 of 97	Medtronic

- 2. Subject did not receive a Medtronic (including Covidien) mesh
- 3. Inability to comply with the mesh IFU
- 4. Subject required more than a single piece of mesh
- 5. Subject has a surgical wound classified as Class II (clean-contaminated), Class III (contaminated) or Class IV (dirty/infected) as defined by the CDC classification
- 6. Subject with an American Society of Anesthesiologists (ASA) score of Class 4, 5, or 6
- 7. Inability to close the hernia defect
- 8. Subject's procedure required a multi-stage repair
- 9. Subject's minimally invasive procedure required to convert to open

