10.7 Operation Requirements

Screening and operative days may be combined if necessary.

The study investigator(s) should perform the elective surgical ventral hernia repair procedure according to the institution's standard of care, the IFUs for both MaxTackTM and the mesh, and the additional requirements noted here. The procedure must be conducted via a minimally invasive approach (conventional laparoscopic or robotic techniques). If the subject met any intraoperative exclusion criteria, the subject will be considered an intraoperative screen failure and will not count toward the total enrollment. The hernia must be repaired with a Medtronic (including Covidien) permanent synthetic mesh that is intended to be used in compliance with the mesh instructions for use, and that is fixated with MaxTackTM. Other criteria for the mesh fixation exclude:

- the use of barbed and conventional sutures applied on the edge of the mesh with a running (simple continuous) suture pattern and/or
- the use of tissue adhesives (glue) in addition to MaxTack fixation.

AFFIX (MaxTa Clinical Invest				
MDT23014	Revision	3.0	Page 41 of 97	Medtronic

The compatibility of Medtronic (including Covidien) meshes with sutured edge fixation and/or tissue adhesives has not been established.

The study procedure includes the necessity to close the hernia defect; in all cases, a minimum of 5 cm overlap over the edges of the initial defect should be achieved superiorly and inferiorly. When possible, a minimum of 5 cm over the edges of the initial defect should be achieved laterally, or at least a mesh coverage of the entire width of the retrorectus/retromuscular compartment is required when applicable. Only a single piece of mesh should be used. The subject should not require a multi-stage repair, and the procedure should not be changed to open. If the procedure cannot be completed with the necessary criteria, the subject will be considered an intraoperative screen failure. If all eligibility criteria are met, the subject will be considered enrolled.

The following procedures and assessments are required to be performed:

- Verification of Subject Eligibility (including intraoperative criteria)
- Medication assessment (prophylactic antibiotics, anticoagulants, antiplatelets, antithrombotic, and/or pain medication)
- Obtain procedure information, including:
 - Operative times
 - General anesthesia information (type)
 - Hernia defect description, defect closure, and surgical technique

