18.8 Appendix H – Surgeon Satisfaction Questionnaire

The Surgeon Satisfaction Questionnaire is a short survey that will be completed after each procedure to evaluate the surgeon's use and satisfaction with MaxTack[™].

AFFIX Study | MaxTack | Surgeon Satisfaction Questionnaire

Surgeon to complete questionnaire immediately after procedure.

To aid in evaluation of performance of the MaxTack[™] Motorized Fixation Device (MaxTack[™]), the study requires that the surgeon performing the ventral hernia repair with MaxTack[™] completes a satisfaction questionnaire immediately after each study procedure.

Subject #:

For this subject's	Please circle	the numb	er that be	est fits you	r answer	
procedure:	Very Difficult	Difficult	Neutral	Easy	Very Easy	N/A
Rate the ease of use of MaxTack [™] to fixate the mesh	1	2	3	4	5	N/A
Rate the ease of maneuverability of MaxTack [™]	1	2	3	4	5	N/A
Rate the ease of using the MaxTack [™] grip / mesh manipulation feature	1	2	3	4	5	N/A

	Please circl	e the number	that best	fits your a	nswer	
For this subject's procedure:	Totally Dissatisfied	Dissatisfied	Neutral	Satisfied	Very Satisfied	N/A
Rate your satisfaction with the force required to fire MaxTack [™]	1	2	3	4	5	N/A
Rate your satisfaction with the performance of MaxTack [™] when fired at different angles (30-60 degrees)	1	2	3	4	5	N/A
Rate your satisfaction with procedure time saving using MaxTack [™] vs. other tackers used for mesh fixation	1	2	3	4	5	N/A
Rate your satisfaction with the overall experience using MaxTack [™]	1	2	3	4	5	N/A

Printed name of Performing Surgeon:

Signature: Date:

	FFIX (MaxTack [™] inical Investigati				
м	DT23014	Revision	3.0	Page 84 of 97	Medtronic

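### No item of the Surgeon Satisfaction Questionnaire directly measures the compatibility that Section 6.1 says it will verify, and its ratings omit cases where a MaxTack device was opened but no tack was placed

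*Protocol*

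**What the plan says.** Section 6.1 of the protocol ends with a list of claims that the study is to verify. One is that MaxTack suits surgeons' techniques and cases, expressed as "ease of use, compatibility with minimally invasive surgical approach(es) assessed using the Surgeon Satisfaction Questionnaire". The endpoint rationale earlier in Section 6.1 also gives compatibility and ease of use as things the endpoints were chosen to evaluate. Section 10.7 allows more than one approach: "The procedure must be conducted via a minimally invasive approach (conventional laparoscopic or robotic techniques", in the protocol's words.

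Appendix H gives the questionnaire in full, seven items each scored 1 to 5 or N/A. Section 10.11 has the operating physician complete it after each procedure.

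Section 9.3 makes it an intraoperative exclusion if no MaxTack tacks were used to fix the mesh. Table 2 in Section 9.4 assigns intraoperative screen failures to no analysis set. Section 10.14.2 keeps only limited data on them, such as the reason for ineligibility, and states that neither adverse events nor device deficiencies are reported. Section 14.2 builds the Full Analysis Set from enrolled subjects who received the device.

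**The concern.** The protocol names two constructs, ease of use and compatibility with the approach, and one instrument to verify both. If that instrument has a question for only one of them, the other claim rests on inference from neighbouring items. Section 4.2 says the data may be used for regulatory and publication purposes, so a claim described as verified will be held against the instrument named for it.

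The second part concerns who is rated. A device that is opened and cannot be made to place a tack is strong evidence against suitability for that case. Under the enrollment rules such a case leaves the ratings and, because deficiencies are not reported for screen failures, the device deficiency endpoint as well. The ratings would then look better than the experience of everyone who tried the device.

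**Working it through.** No sample size, power or alpha figure is involved, so there is no stated figure to reproduce. The check is a comparison of texts.

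**Step 1: the seven Appendix H items against the two constructs in Section 6.1.**

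| Item | Content | Bearing on the claim |
|---|---|---|
| 1 | Ease of use in fixating the mesh | Direct measure of ease of use |
| 2 | "Rate the ease of maneuverability of MaxTack" | Indirect for compatibility |
| 3 | Ease of the grip / mesh manipulation feature | A device feature |
| 4 | "Rate your satisfaction with the force required to fire MaxTack" | A device feature |
| 5 | Satisfaction with performance "when fired at different angles (30-60 degrees" | Indirect for compatibility |
| 6 | "Rate your satisfaction with procedure time saving using MaxTack", against other tackers | Time |
| 7 | Overall experience | Global |

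Count: ease of use has a direct item (1 of 7). Compatibility with the approach has none (0 of 7) and two indirect ones (items 2 and 5). The form has no field for laparoscopic or robotic approach. Section 10.7 does collect surgical technique on the operative form, so the split can be made from data already held.

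**Step 2: three kinds of case followed through the enrollment rules.**

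- *Device opened, at least one MaxTack tack used, no intraoperative exclusion met.* Enrolled (Sections 6 and 15.1), in the Full Analysis Set (Section 14.2), rated, and deficiencies on the day of surgery counted (Section 5.2.2). This holds even if the device gave trouble, or if a second MaxTack device was needed.
- *Device opened, no MaxTack tack placed, mesh fixed another way.* Meets intraoperative exclusion 1 (Section 9.3); analysis set none (Table 2); no deficiency reported (Section 10.14.2). A battery problem, which Section 5.2.2 gives as an example of a deficiency, would be lost from the endpoint if it led to this outcome.
- *"minimally invasive procedure required to convert to open".* Meets intraoperative exclusion 9 and is handled in the same way, whatever the cause.

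**Step 3: size.** The protocol gives no expected number of opened-but-unused devices. If k such cases occur beside 110 enrolled, the share of these cases left out of the ratings is k / (110 + k). With k as a pure assumption:

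- k = 3: 3/113 = 2.7%
- k = 6: 6/116 = 5.2%
- k = 11: 11/121 = 9.1%

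How the omitted cases would have been scored is unknown, so no effect on a mean rating is calculated.

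**The case against.** The strongest reply is that the questionnaire is not silent on compatibility. Its items refer to that subject's procedure, and every rated procedure was completed by a minimally invasive approach. Ratings of fixating the mesh, maneuvering the device and firing at an angle therefore describe how it worked within that approach. This stands in part. It rules out saying that compatibility goes wholly unassessed, but it does not supply the direct measure that Section 6.1 implies.

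A reader might also infer that only cases where the device was used to completion are rated. The documents do not support that. Enrollment needs one tack, Section 10.7 collects data on other fixation, and the fixation methods it rules out are running edge sutures and tissue adhesives. A surgeon who places one tack, struggles and finishes by another permitted method is still enrolled and rated.

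A reader might count conversions to open surgery as device failures. Nothing in the protocol links conversion to the device, and a conversion before fixation would yield mostly N/A answers.

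Nor do unused devices vanish from the record. The accountability log is updated when a device is opened (Section 7.7), the reason for screen failure is recorded (Section 10.14.2), a CONSORT diagram is planned (Section 14.1), and product complaints are reportable with no stated exemption for screen failures (Section 12.6). All of this stands, but none of it brings these cases into the ratings or the deficiency endpoint.

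Finally, tabulating ratings by approach is a matter for the statistical analysis plan, which is not at hand; its absence from the protocol is no fault. The plan cannot, however, create a missing item or recover forms that were never collected.

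**Conclusion.** The point holds in a limited form. Section 6.1 promises to verify compatibility with an instrument that has no direct item for it (0 of 7 direct, 2 of 7 indirect). The ratings also omit cases in which a device was opened and no tack was placed; these are likely to be the least favourable to the device, although some may have causes unrelated to it. The size of that omission cannot be derived from the protocol, and the shares above rest on assumed counts.

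The consequence is confined to the compatibility and ease-of-use claim. Surgeon satisfaction is a descriptive secondary endpoint with no success threshold, Section 14.8 plans a single hypothesis test, and the primary analysis is not affected. The change is still worth making because it is cheap and has to be in place before the cases are performed.

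**What to change.** Preferred change:

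1. Add one Appendix H item asking how compatible MaxTack was with the approach used in that case.
2. Have the form completed for every case in which a MaxTack device was opened, including intraoperative screen failures.
3. Summarise the opened-but-not-used cases separately, with the reason, beside the Full Analysis Set summary. Keeping them separate leaves the enrollment definition and analysis sets unchanged.
4. Show the ratings by laparoscopic versus robotic approach, from the technique data already collected.

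Alternative: remove compatibility from the Section 6.1 claim and limit what remains to cases with at least one tack placed and the repair completed minimally invasively.

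The cost of the preferred change is one extra item and a few extra forms. Surgeons already complete the form after each procedure, and the accountability log already identifies opened devices. The alternative costs only an edit to the text.

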7.1 General

MaxTack[™] Motorized Fixation Device is composed of three main subsystems: the tack and the delivery system, which includes the shaft and handle (Figure 1).

The tack is the fixation implant delivered by the device to secure the hernia mesh to the tissues. The tack is constructed of an absorbable synthetic polyester copolymer derived from lactic and glycolic acid. The

AFFIX (MaxTac Clinical Investi				
MDT23014	Revision	3.0	Page 27 of 97	Medtronic

first 25 tacks are dyed with D&C Violet No. 2. The last 5 tacks are dyed with D&C Green No. 6 to serve as an indicator of low tack count to the user. The total tack length (including tack head) is 7 mm.

The distal portion of the shaft is inserted into the cannula and into the patient's body cavity. The shaft contains the tacks and the drive mechanism that deploys and advances the tacks. The distal end of the shaft has a mesh manipulation/grip feature that may be used to help facilitate the positioning of the mesh.

The handle is the interface that the user grips when using the device. The handle contains a single motor assembly, printed circuit board assembly (PCBA) with microprocessor, encoder, light-emitting diode (LED) indicator, speaker, tactile switch, and two 9V alkaline batteries in parallel. The motor within the handle provides the mechanical torque controlled by the PCBA for tack deployment. The LED and speaker provide device status information to the user through visual lights and audible tones. When the trigger pushbutton firing mechanism is depressed, tack deployment is initiated by the software stored in the microprocessor. The PCBA has an encoder to provide shaft position information. The software controls the motor speed and position using encoder pulses. As the motor rotates, tacks advance through the drive system of the shaft and a single tack is deployed into the desired tissue (Figures 2, 3 and 4).

[figure not shown]

Figure 1: MaxTack[™] Motorized Fixation Device Overview

[figure not shown]

Figure 2: MaxTack[™] Motorized Fixation Device Handle Internal Assembly – 1

[figure not shown]

Figure 3: MaxTack[™] Motorized Fixation Device Handle Internal Assembly – 2

[figure not shown]

Figure 4: MaxTack[™] Motorized Fixation Device Handle Internal Assembly

AFFIX (MaxTa Clinical Invest				
MDT23014	Revision	3.0	Page 29 of 97	Medtronic

According to ISO 10993-1, the MaxTack[™] Motorized Fixation Device is an implantable device (absorbable tacks) in long-term contact (> 30 days) with tissues. The absorbable tacks do not contain any medicinal substances, animal tissues, or blood components.

MaxTack[™] involves an implantable component, which is absorbable. The tack is made up of a copolymer poly (glycolide-co-L-lactide) (PGLA). This copolymer degrades and is absorbed by hydrolysis to glycolic acid and lactic acid, which are then metabolized by the body. The absorption profile of PGLA in the first two weeks after initial implantation is minimal, with significant absorption from three to five months. Following this significant breakdown, the polymer absorption is essentially completed prior to one year.

In view of the detailed consideration of all the relevant data, the biological safety evaluation of MaxTack[™] has been found compliant with the biological safety requirements of ISO 10993-1, Ministry of Health, Labor and Welfare (MHLW) and FDA guidance on the use of International Standard ISO 10993-1, "Biological evaluation of medical devices - Part 1: Evaluation and testing within a risk management process".

All materials that may contact tissues and/or body fluids are presented in Table 1.

MaxTack [™] Motorized	Materials	Subject Contact	
Fixation Device Component			
Shaft	304L Stainless Steel with laser etched logo	Limited subject contact (less than 24 hours)	
Implant (Tack)	L1 Polymer: Absorbable Synthetic Polyester [poly (glycolide-co-L-lactide) (PGLA)]	Greater than 30 days	

Table 1: Materials in Contact with Tissues and/or Body Fluids

At the time of document approval, $MaxTack^{TM}$ is 510(k) cleared in the United States (US). There is no anticipated change in the product during the course of the study.

7.3 Packaging

MaxTack[™] devices used in this study will be packaged in accordance with released product standards as single-use sterile devices. Each device will be individually packaged within a PETG tray with a Glidex lid. A

AFFIX (MaxTack [™] Motorized Fixation Device) Clinical Investigation Plan				
MDT23014	Revision	3.0	Page 30 of 97	Medtronic

desiccant is taped outside of the tray. The device and tray are placed and sealed in a foil pouch packaging system (TYVEK-UNCOATED 1073B PERFECFLEX 35678-G foil pouch with breather stamp). For secondary packaging, one primary package including Instruction for Use (IFU) is inserted into a CLAY COATED NEWSBACK straight tuck display box, which will be sealed with two round Pilfer labels on each end. The display box will also be labeled appropriately.

Device packaging will contain Instructions for Use as noted in Section 18.6, Appendix F – Instructions for Use. The device labeling will be provided in English and/or local language upon requirements in the countries participating in the study.

7.4 Intended Population

The MaxTack[™] Motorized Fixation Device is indicated for use in the fixation of prosthetic material to soft tissue in minimally invasive ventral and minimally invasive groin hernia repair procedures. The intended purpose of the device is the fixation of prosthetic material. The study only includes the population of subjects undergoing minimally invasive ventral hernia repair procedures and those meeting the study eligibility criteria listed in Section 9.

Further information on contraindications can be found in the device instructions for use, Section 18.6, Appendix F – Instructions for Use.

7.5 Equipment

No equipment is required to assess the endpoints in the AFFIX study. However, at the physician's discretion, imaging (e.g., CT scan, ultrasound exam, MRI) may be used to confirm hernia recurrence if this is the site standard of care. Any equipment for assessing hernia recurrence will be used/maintained/calibrated according to the study site's standard protocol. The maintenance and calibration report should be made available to monitors upon request. Since the use of such equipment is not required per protocol and may differ by site, Medtronic will not monitor maintenance and calibration of equipment.

7.6 Product Training Materials

Investigator(s) and study staff participating in the clinical study and the associated clinical study staff will receive training on the clinical study protocol by the Medtronic study teams prior to performing study activities. Each Investigator performing a study procedure will receive training on using the MaxTack[™] Motorized Fixation Device by an authorized Medtronic representative, in addition to device characteristics, shelf life, storage requirements, device use, warnings, precautions, and contraindications. As the device is commercially available and is very similar to other tackers on the market, this training may occur after the site's study activation and during the physician's first case.

